### **Source and composition of tocotrienol**

Tocotrienol mixture derived from palm oil will be used. It will be sponsored by Hovid Sdn Bhd (Ipoh, Malaysia). The composition of the tocotrienol mixture is 24.7%  $\alpha$ -tocotrienol, 4.5%  $\beta$ -tocotrienol, 36.9%  $\gamma$ -tocotrienol, 12.0%  $\sigma$ -tocotrienol and 21.6%  $\alpha$ -tocopherol. It is formulated with a self-emulsifying system (SES) to enhance absorption of tocotrienol.

The gelatin sheet used in the manufacturing of tocotrienol soft gel capsules is prepared using gelatin derived from a bovine source.

### **Dosing of tocotrienol**

Animal studies reported that a dose of 60 mg/kg tocotrienol could be effective in maintaining liver health [16]. To extrapolate this to human equivalent dose, body surface conversion (24) is used:

#### Human equivalent dose (HED)

$$= [\text{Km rat/Km human}] \times [\text{dose in rat}] \times [\text{expected body weight of humans}]$$

$$= [6 / 37] \times [60 \text{ mg/kg}] \times [60 \text{ kg}]$$

$$= 584 \text{ mg} \approx 600 \text{ mg}$$

However, this calculation does not consider the bioavailability-enhancing effect of SES. A previous study showed that the use of SES enhanced the bioavailability of tocotrienol by 4-fold [25]. Notwithstanding that, the effects of SES on the tissue distribution of tocotrienol, especially in the musculoskeletal system are not well-known. Therefore, we propose to use 400 mg (a decrease of 33.3% from the original calculated dose) in the trial subjects.

It will be packaged into two soft gels, each containing 200 mg palm tocotrienol. One soft gel will be taken orally, daily after breakfast and dinner to complete the 400 mg daily dose. The treatment period will be 6 months. The placebo will consist of equivolume refined, bleached, and deodorised (RBD) palm olein. Both tocotrienol and placebo capsules will be manufactured in accordance with any applicable GMP, and is coded and labeled in a manner that protects the blinding. In addition, the labeling should comply with applicable regulatory requirement(s).

### **Dispense of TRF**

Since the study activity for each subject will last for six months, either TRF or placebo with identical appearance and packaging will be dispensed to the subjects twice, which is every three months (during baseline and visit 1). There is a  $\pm 7$ -day allowable window period for visit 1 as some subjects might not be able to turn up on the exact visit date. Softgel counting will be

performed at visit 1 and 2 to determine the compliance of the subjects. Subjects will be requested to consume the softgel after meal.

### **“Stopping rules” or “discontinuation criteria**

The participation of the trial subjects will be terminated if they cannot adhere to alcohol abstinence and cannot comply with the treatment regimes. Failure to adhere is a serious problem that not only affects the subjects but also the overall conduct and outcome of the research. They will also be stopped from participating in situations where the risks outweigh the anticipated benefits, in cases of severe allergic reactions or any adverse events that occurred in individual trial subjects. Subjects in these trials should be particularly closely monitored and should be withdrawn if they appear to be unduly distressed.

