### **Withdrawal criteria**

During the course of the trial a subject may choose to withdraw early from the trial treatment at any time. This may happen for a number of reasons, including but not limited to:

- The occurrence of what the participant perceives as an intolerable adverse event (AE).
- Inability to comply with trial procedures
- Participant decision

Subjects may choose to stop their participation, and it will not affect their treatment at UKM-affiliated hospitals and clinics in any way. Without losing any of their rights as patients, they will not be penalised and can still continue with the standard treatment available and for follow-up visits at UKMMC. The data and samples already collected would not be used in the final study analysis and would be discarded.

In addition, we may discontinue a participant from the trial treatment at any time if we consider it necessary for any reason including, but not limited to:

- Pregnancy
- Ineligibility (either arising during the trial or retrospectively having been overlooked at screening)
- Significant non-compliance with treatment regimen or trial requirements
- An adverse event which requires discontinuation of the trial medication or results in inability to continue to comply with trial procedures

- Disease progression which requires discontinuation of the trial medication or results in inability to continue to comply with trial procedures

We have adjusted our sample size calculation for this study by considering the risk of dropout among the subjects. Hence, the withdrawn subjects will not be replaced while ensuring that the minimal sample size of this study is achieved. The type of withdrawal and reason for withdrawal will be recorded in the CRF. If the participant is withdrawn due to an adverse event, we will arrange them for follow-up visits at our clinic until the adverse event has resolved or stabilised.

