### **Adverse Events (AEs), Serious Adverse Events (SAEs), and Suspected Unexpected Serious Adverse Reactions (SUSARs)**

While the possibility of having some unwanted side effects and unexpected events related to the tocotrienol supplementation and the treatment procedures is very low, the enrolled subjects should still be aware of the possibility. We will try to decrease the chances of this event occurring through close monitoring of all subjects but if something unexpected happens, we will provide them with proper care and appropriate treatment. We may use some other medicines to decrease the symptoms of the side effects or reactions. Or we may stop the use of this supplement and end their participation. If this is necessary, we will discuss it with the

subjects, and they will always be consulted before we move on to the next step. Given that the subjects must adhere to alcohol abstinence throughout the course of this study, if they experience any withdrawal symptoms, we will give them supportive care and medications as part of the treatment regimens used in alcohol withdrawal states to minimise the symptoms and prevent complications.

Our qualified physician, who is a co-investigator for the trial, will be responsible for all trial-related medical decisions. During and following a subject's participation in this trial, we will ensure that adequate medical care is provided to a subject for any adverse events, including clinically significant laboratory values, related to the trial. We will inform a subject when medical care is needed for intercurrent illness (es) of which we become aware. We will also recommend the subjects to inform their primary physician about their participation in this trial if the subject has a primary physician and if the subject agrees to the primary physician being informed, while fully respecting the subject's rights.

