#### Reporting Procedures for Adverse Events

Adverse events and/or laboratory abnormalities identified as critical to safety evaluations will be reported to the sponsor according to the reporting requirements and within the specified time periods.

All AEs occurring during the trial that are observed by the Investigator or reported by the trial subject will be reported on the trial case report form (CRF), whether or not attributed to trial medication. The following information will be reported on the CRF: description, date of onset and end date, severity, assessment of relatedness to trial medication, other suspect drug or device and action taken. Follow-up information should be provided as necessary.

The severity of events will be assessed on the following scale: 1 = mild, 2 = moderate, 3 = severe.

Non-serious AEs considered related to the trial medication as judged by a medically qualified investigator or the Sponsor will be followed up either until resolution, or the event is considered stable.

It will be left to the clinical judgment of our medical officer to decide whether or not an AE is of sufficient severity to require the participant's removal from treatment. A participant may also voluntarily withdraw from treatment due to what he or she perceives as an intolerable AE. If either of these occurs, the participant will be given appropriate care under medical supervision until symptoms cease, or the condition becomes stable.

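### Withdrawal rules discard collected data and end participation, so randomised subjects leave the analysis because of events after randomisation

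*Protocol*

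**What the plan says.** Protocol, *Withdrawal criteria*, first deals with subjects who decide to stop. It lists three non-exhaustive reasons: an AE the subject finds intolerable, inability to comply with procedures, and the subject's own decision. The paragraph that follows protects the subject's right to leave and closes with: "The data and samples already collected would not be used in the final study analysis and would be discarded".

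The same section then turns to discontinuation by the investigators. One ground is "An adverse event which requires discontinuation of the trial medication or results in inability to continue to comply with trial procedures". No discard sentence is attached to that list. On replacement it says: "Hence, the withdrawn subjects will not be replaced while ensuring that the minimal sample size of this study is achieved". For AE withdrawals it adds: "we will arrange them for follow-up visits at our clinic until the adverse event has resolved or stabilised".

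Protocol, *Stopping rules or discontinuation criteria*, ends participation for failed abstinence and non-compliance. It then says subjects will "also be stopped from participating in situations where the risks outweigh the anticipated benefits, in cases of severe allergic reactions or any adverse events".

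Two other sections are softer. *Adverse Events, Serious Adverse Events, and SUSARs* says: "Or we may stop the use of this supplement and end their participation". *Reporting Procedures for Adverse Events* says: "It will be left to the clinical judgment of our medical officer to decide whether or not an AE is of sufficient severity" to require removal from treatment. It promises care until symptoms cease or the condition is stable.

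**The concern.** Stopping the product and leaving the study are different events, and the protocol merges them. The withdrawal section opens by speaking of withdrawal from trial treatment, yet its consequence is that outcome data are destroyed. The stopping rules end participation where stopping the capsules would do.

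Two kinds of loss follow:

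- A subject who chooses to stop loses everything already collected, including the baseline and any month-3 result.
- A subject whom the investigator stops under the stopping rules loses the outcomes still due. Only safety follow-up is provided after an AE.

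Both losses depend on what happens after randomisation. The analysed groups are then no longer the groups that were randomised. The discard is a stated rule, so a statistical analysis plan could define an analysis set but could not bring the data back. With 13 per arm, each lost subject is about 8% of an arm (1/13), and subjects who leave are not replaced.

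**Working it through.** **1. The plan's own figure.** Inputs from *Sample Size Calculation*: means 12.82 and 3.86, SD 7.0, z-values 1.96 and 0.84, 20% loss.

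- Difference = 12.82 − 3.86 = 8.96.
- n = (1.96 + 0.84)² × 2 × 7.0² / 8.96² = 7.84 × 98 / 80.28 = 9.57, rounded up to 10 per arm.
- 10 / 0.8 = 12.5, rounded up to 13 per arm, 26 in total.

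The stated figures reproduce. The allowance is three subjects per arm.

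**2. What each rule removes.**

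| Route out | Data already collected | Outcomes still due |
|---|---|---|
| Subject chooses to stop | discarded (stated) | lost |
| Stopped under the stopping rules | no discard stated | participation ends; after an AE only safety follow-up is provided |

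**3. Size of the loss.** The protocol gives no AE removal rate, so p is assumed. It is equal in both arms and the only source of loss. The number left in each arm is Binomial(13, 1 − p). Power is that of the two-sided two-sample t-test (noncentral t, difference 8.96, SD 7.0, alpha 0.05), averaged over the arm sizes.

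| p | Mean left per arm, 13(1 − p) | Average power | P(both arms ≥ 10) |
|---|---|---|---|
| 0% | 13.00 | 0.879 | 1.000 |
| 2% | 12.74 | 0.871 | 0.9998 |
| 5% | 12.35 | 0.859 | 0.994 |
| 10% | 11.70 | 0.836 | 0.933 |
| 20% | 10.40 | 0.782 | 0.558 |
| 30% | 9.10 | 0.714 | 0.177 |

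Average power falls to 0.80 at p = 17%. If AE removal came on top of a separate 20% loss, so that the share left is 0.8(1 − p), power at 10/20/30% would be 0.729/0.666/0.593.

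**4. What following everyone would do to power.** Simulated trials with 13 per arm, all followed. Each tocotrienol subject is off product with probability p and keeps a share r of the 8.96 effect.

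| p | r = 0 | r = 0.5 | r = 1 |
|---|---|---|---|
| 2% | 0.86 | 0.87 | 0.88 |
| 5% | 0.83 | 0.86 | 0.88 |
| 10% | 0.77 | 0.84 | 0.88 |
| 20% | 0.65 | 0.79 | 0.88 |
| 30% | 0.53 | 0.74 | 0.88 |

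If off-product subjects lose the whole effect, power is lower than under removal (0.77 against 0.84 at 10%). If they keep half of it, power is about equal or slightly higher. Retention restores the randomised comparison. It does not guarantee power.

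**The case against.** The strongest reply is that this reads loose drafting harshly. The words on any adverse events follow a risk-benefit condition that may be meant to limit them. The investigator part of *Withdrawal criteria* and *Reporting Procedures for Adverse Events* speak of stopping treatment, at clinical judgement. *Treatment of Subjects* requires each subject to attend three-monthly follow-up and makes no exception for those off product. The discard sentence sits in a paragraph on subjects' rights and may be meant only for people who leave the study. Side effects are described as very unlikely, and 20% loss is already budgeted.

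Much of this stands:

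- A reader might infer that every AE forces removal. The other AE sections make that improbable.
- A reader might infer that the discard rule covers subjects whom the investigators stop. The text does not say so.
- The investigator-stop half therefore rests on looser wording than the discard half.
- At removal rates near the protocol's own expectation, the loss of power is negligible.

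The reply does not remove the discard rule. It is explicit, its listed reasons include inability to comply and an intolerable AE, and it makes no reference to the subject withdrawing consent to use of the data. The stopping rules still end participation on any reading, and no section says that subjects stopped for an AE keep their outcome visits. The dropout allowance protects the count. It does not protect the comparison as randomised.

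**Conclusion.** The point holds and is minor. The firm part is the discard rule: data are deleted because of an event after randomisation, for any of the subject's reasons for stopping. The weaker part is that the stopping rules end participation where stopping the product would be enough.

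At an assumed 2 to 30% removal, equal in both arms, average power runs from about 0.87 down to 0.71, against 0.88 with no loss. It stays at 0.80 or above up to about 17% removal. The effect is small within the 20% allowance and would matter if removal exceeded that or added to other loss. These figures rest on the protocol's difference and SD and on assumed removal rates.

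A reader might go further and infer that the arms will lose subjects unequally, that the result will be biased in a known direction, or that the trial is underpowered for this reason. The documents give no AE rate by arm and do not support any of these. What is shown is a departure from the comparison as randomised and an avoidable loss of data.

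**What to change.** 1. *Withdrawal criteria*: replace the discard sentence. Data already collected are kept and analysed as randomised, whatever the reason for stopping, unless the subject withdraws consent to their use. Limiting this to AEs would leave the same rule in force for own decision and inability to comply.
2. *Stopping rules or discontinuation criteria*: say that an AE stops the study product when the medical officer judges it necessary, in line with *Reporting Procedures for Adverse Events*. The already planned month-3 and month-6 assessments are kept if the subject agrees.

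The cost is a wording amendment in two sections and no new visits. Some off-product subjects will decline to attend. The consent pages are not available here. If they repeat the promise to discard, they need the same change, and subjects already enrolled under that promise would have to be asked.

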### **Accountability procedures for TRF product and placebo**

We will take the responsibility for TRF product and placebo accountability at the trial site. The records of the product's delivery to the trial site, the inventory at the site, the use by each subject, and the return to the sponsor or alternative disposition of unused product will be maintained. These records should include dates, quantities, batch/serial numbers, expiration dates and the unique code numbers assigned to the TRF and placebo products and to trial subjects. We will maintain the records that document adequately that the subjects were provided the doses specified by the protocol and reconcile all investigational product received from the sponsor. The products will be stored in accordance with applicable regulatory requirements, and will be ensured that they are used only in accordance with the approved protocol. We will explain the correct use of the products to each subject and will check, at intervals appropriate for the trial, that each subject is following the instructions properly.

### **Maintenance of trial treatment randomization codes and procedures for breaking code**

We will follow the trial's randomization procedures, and will ensure that the code is broken only in accordance with the protocol. Given that the trial is blinded, we will promptly document and explain to the sponsor any premature unblinding (e.g., accidental unblinding, unblinding due to a serious adverse event) of the investigational product. We will have a written procedure for rapidly identifying a ‘blinded’ IP in case of an emergency. The procedure will be secure, readily available at all times during the trial, and not allow breaks of the blinding to go undetected.

### **Data recorded directly on the CRFs is to be considered the source data.**

We will maintain adequate and accurate source documents and trial records that include all pertinent observations on each of the site’s trial subjects. Source data should be attributable, legible, contemporaneous, original, accurate, and complete. Changes to source data should be traceable, should not obscure the original entry, and should be explained if necessary (via an audit trail). We will ensure the accuracy, completeness, legibility, and timeliness of the data reported to the sponsor in the CRFs and in all required reports. Data reported on the CRF, that are derived from source documents, should be consistent with the source documents or the discrepancies should be explained. Any change or correction to a CRF will be dated, initialed, and explained (if necessary) and will not obscure the original entry (i.e. an audit trail should be maintained); this applies to both written and electronic changes or corrections. Records of the changes and corrections will be retained.

We will maintain the trial documents as specified in Essential Documents for the Conduct of a Clinical Trial in the Malaysian Guideline for Good Clinical Practice and as required by the applicable regulatory requirement(s). Measures that prevent accidental or premature destruction of these documents will be taken. All the essential documents will be retained until at least 2 years or for a longer period, if required by the applicable regulatory requirements. We will make available for direct access all requested trial-related records, upon request of the monitor, auditor, IRB/IEC, or regulatory authority.

## **SELECTION AND WITHDRAWAL OF SUBJECTS**

### **Inclusion criteria:**

1. Patients with history of alcoholic use disorder with clinical and biochemical evidence of alcoholic steatohepatitis.
2. Patients with Maddrey's discriminant function  $\leq 32$ , and do not require the treatment of corticosteroid therapy or pentoxifylline.
3. Patients aged 18 to 65
4. Patients who could comply with alcohol abstinence.

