Acetaldehyde is also postulated to play an etiologic role in alcoholic liver disease as it forms adducts with reactive residues on proteins or small molecules like cysteine [5]. These chemical modifications can alter or interfere with normal biological processes resulting in formation of substances such as acetaldehyde and malondialdehyde (MDA). The formation of MDA antigens during alcohol-induced liver disease likely contributed to the immunologic reaction associated with alcohol related liver damage [6]. Acetaldehyde has also been shown to impair mitochondrial glutathione transport and to sensitize hepatocytes to TNF-mediated killing. Lastly, acetaldehyde disrupts intestinal barrier function leading to endotoxemia and proinflammatory cytokine production.

Oxidative stress in the liver also increases after alcohol consumption. In hepatocytes, CYP2E1 activity increases after alcohol consumption [7]. The CYP2E1 system leaks electrons which initiate the oxidative stress [8]. Other sources of oxidative stress are infiltrating inflammatory cells in the liver. Oxidative stress in alcoholic liver disease is documented by detection of protein oxidation (eg: protein thiol or carbonyl products), lipid oxidation (eg: MDA), DNA oxidation (eg: oxodexyguanosine) or depletion of antioxidant defences (eg: vitamin E, glutathione, thioredoxin) [8]. Therefore, antioxidant supplementation could be a useful adjunct in the treatment of alcoholic hepatitis.

Diagnosis of alcoholic liver disease:

AFLD is currently defined by steatosis with a range of hepatic histopathologic changes including the presence of inflammatory infiltrates and varying degrees of fibrosis and cirrhosis that develop in the presence of chronic alcohol consumption, which is a known trigger factor that causes fat accumulation. Despite having comparable pathophysiological spectrum, the distinction between AFLD and NAFLD is determined by the amount of alcohol ingested, with AFLD being diagnosed based on the patient's history of regular alcohol usage, defined as >30 g/day in males and >20 g/day in females (according to clinical practice guidelines from the scientific associations for the study of liver diseases) [9, 10].

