Apart from a reliable history of significant alcohol intake, no single laboratory or imaging testing can definitively confirm the diagnosis of ALD. Hence, its diagnosis is based on the compilation of clinical findings of hepatomegaly with signs of chronic liver disease, radiographic evidence of liver steatosis, fibrosis or cirrhosis, combined with abnormal biochemical results suggestive of liver injury [11].

Meanwhile, NAFLD is closely linked to obesity, caused by excessive food intake with a high-calorie, high-fat diet combined with a sedentary lifestyle [12, 13]. Most often, it is also associated with metabolic dysfunction [11, 14]. Obese people are more likely to develop

metabolic syndrome, and nonalcoholic fatty liver disease (NAFLD) has been identified as the hepatic manifestation of metabolic syndrome [15].

Therefore, in the context of this study, we propose to exclude the subjects who are obese (a body mass index (BMI) of 30 kg/ m^2 or higher) and with metabolic syndrome (based on the harmonised criteria) to minimise the risk of misclassification between AFLD and NAFLD.

Clinical evidence of decompensated liver disease such as ascites and its severity, hepatic encephalopathy; severity according to West Haven criteria, jaundice and coagulopathy must be assessed for. Evidence of alcoholic hepatitis as demonstrated by hepatocellular transaminitis of AST:ALT > 2:1 due to deficiency of pyridoxal 5'phosphate level in alcoholic patients, raised gamma glutamyl transpeptidase (GGT) raised mean corpuscular volume (MCV), raised total bilirubin with severely ill patients having coagulopathy as demonstrated by raised international normalised ratio (INR) and prothrombin time (PT). Patients with other forms of bleeding disorder, as well as those on anticoagulant or antiaggregant treatments are not eligible to participate in the trial. Patients who have been taking vitamin E, herbal supplements or other investigational products are also excluded.

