## SAMPLE SIZE CALCULATION

Sample size calculation was based on the comparison of two means derived from the effects of tocotrienol on fatty liver index (FLI) in patients with non-alcoholic fatty liver disease (NAFLD) (21). This is because the effectiveness of tocotrienol in alcoholic hepatitis has not been evaluated previously.

Formula of calculating sample size in clinical trial (22):

$$n = [(Z\alpha/2 + Z\beta)^2 \times \{2(\sigma)^2\}] / (\mu_1 - \mu_2)^2$$

Where:

$n$  = sample size required in each group

$\mu_1$  = mean of FLI for tocotrienol group = 12.82  $\mu_2$  = mean of FLI for placebo group = 3.86

$\sigma$  = standard deviation = 7.0

$Z\alpha$ : This depends on level of significance, for 5% this is 1.96  $Z\beta$ : This depends on power, for 80% this is 0.84

$$n = [(1.96 + 0.84)^2 \times \{2(7.0)^2\}] / (12.82 - 3.86)^2$$

The sample size calculated is 10 per group. Taking into account 20% of subjects might be lost to follow up, the number of each group is adjusted to 13. Hence, the total sample size required for this study is 26 individuals.

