## **SCREENING**

Primarily we will be recruiting adult patients who fulfil all the inclusion criteria of this study, who come for follow up in Gastroenterology & Hepatology clinic in Hospital Canselor Tuanku Muhriz UKM (HCTM). Additionally, our research subjects were also recruited from the general public who responded to our recruitment poster in the hospital and on social media platforms. Subjects will answer a questionnaire on their demographic and lifestyle details, medical and medication history. Their alcohol consumption behaviour will be surveyed using the AUDIT questionnaire. A qualified physician will perform physical examination on the subjects. The AUDIT questionnaire (23) is a 10-item screening tool used to identify individuals with harmful drinking behaviour. A score of 8 or more indicates harmful or hazardous drinking behaviour. In addition, patients will be screened for clinical (signs and symptoms of alcoholic liver disease such as parotid swelling, hepatomegaly and clinical evidence of cirrhosis) and biochemical evidence of alcoholic liver disease (transaminitis, AST:ALT ratio >2.0, raised gamma glutamyl transferase (GGT), mean corpuscular volume (MCV) and total bilirubin).

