### **Ultrasound**

Ultrasound of the hepatobiliary system will be performed during initial recruitment to rule out the presence of hepatocellular carcinoma (HCC) which can occur in patients with alcoholic liver cirrhosis. During the screening an ultrasound probe will be placed in the patients' right hypochondrium to assess for any abnormal lesions representative of HCC. It is a non-invasive procedure which takes approximately 20 minutes. Patients with hepatocellular carcinoma will be excluded from the study.

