### **Fibroscan**

This is a non-invasive test to measure liver stiffness, kPa (indicator of liver fibrosis) and to detect degree of fat accumulation (CAP range value of 100-400 dB/m). Liver stiffness of > 8kPa indicates advanced fibrosis while CAP of > 263 indicates fatty liver. During the screening, the patient will lie down on the examination bed with his/her right hand behind

his/her head. Investigator will place the probe between the right ribs of the patient. Measurements will be recorded into the machine (FibroScan® 502 Touch). The screening is quick, easy and non-invasive and usually takes less than 15 minutes.

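### The protocol defines alcoholic fatty liver disease by steatosis, but no objective steatosis requirement reaches the written eligibility criteria or the available text of the diagnostic algorithm

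*Protocol*

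**What the plan says.** The intended population is clear from the narrative. The Project Synopsis states that "AFLD is currently defined by steatosis with a range of hepatic histopathologic changes". Both the Methodology section and the background on the investigational product speak of recruiting patients who carry an AFLD diagnosis.

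The operative text is different:

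- **Inclusion criterion 1** asks for "Patients with history of alcoholic use disorder with clinical and biochemical evidence of alcoholic steatohepatitis".
- **Screening** spells out that evidence. The clinical signs are parotid swelling, an enlarged liver and signs of cirrhosis. The laboratory findings are raised transaminases, AST:ALT above 2.0, and raised GGT, MCV and bilirubin.
- **Exclusion criteria** contain no item that removes a patient without steatosis.
- **Algorithm of Diagnosis of Alcoholic Hepatitis** lists FibroScan and FibroTest under advanced fibrosis or cirrhosis, and ultrasound for hepatocellular carcinoma. The Ultrasound section gives the same single purpose.
- **Fibroscan** describes a scan done at screening and states "Liver stiffness of > 8kPa indicates advanced fibrosis while CAP of > 263 indicates fatty liver". No criterion uses the CAP value.
- **Recruitment** is not confined to clinic patients: "our research subjects were also recruited from the general public who responded to our recruitment poster".

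The Sample Size Calculation rests on an FLI difference taken from a study in patients with non-alcoholic fatty liver disease, that is, in people who had fatty liver.

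**The concern.** Eligibility criteria decide who is in the trial, and here they do not carry the named disease into enrolment. Take a volunteer who answers a poster and has an enlarged liver, raised GGT, AST:ALT above 2, a Maddrey score within the limit and a CAP of 210 dB/m. This person can meet every numbered criterion, yet by the Fibroscan section's own threshold is not classed as having fatty liver.

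Two things are at stake. First, the planned FLI difference comes from patients with liver fat to lose, so entrants without it would be expected to shrink the average contrast. Second, conclusions about AFLD weaken if some participants do not have it by the protocol's definition. With 13 per arm, even a few such entrants count, and their baseline status cannot be changed once they are randomised.

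**Working it through.** **Step 1. Compare the definition with the entry rule.** The definition of AFLD requires steatosis. Criterion 1 requires clinical and biochemical evidence, and every item listed for it in Screening is a physical sign or a blood test. For the wider category of alcoholic liver disease, the Project Synopsis describes a compilation of clinical findings, imaging and biochemistry. Criterion 1 keeps the first and third of these and leaves out imaging.

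**Step 2. Look for steatosis elsewhere in the entry path.** The algorithm assigns FibroScan to fibrosis or cirrhosis and ultrasound to liver cancer. The Treatment of Subjects section places a liver scan at the initial screening visit. The measurement therefore exists but is not tied to entry.

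**Step 3. Reproduce the plan's sample size.** Inputs from the Sample Size Calculation:

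- Group means 12.82 and 3.86, so the difference is 8.96.
- SD 7.0.
- For Zα, "This depends on level of significance, for 5% this is 1.96"; for Zβ, "This depends on power, for 80% this is 0.84".
- Loss to follow-up 20%.

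n = (1.96 + 0.84)² × 2 × 7.0² / 8.96² = 7.84 × 98 / 80.28 = 9.57, so 10 per group.

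With losses, 10 / 0.8 = 12.5, so 13 per group and 26 in total. The stated figure reproduces.

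**Step 4. Power with 10 evaluable per group, using the plan's normal formula.**

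SE = 7.0 × √(2/10) = 3.13

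Power = Φ(8.96/3.13 − 1.96) = Φ(0.90) = 0.817

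**Step 5. Illustrate dilution.** Let f be the share of patients without steatosis, assumed equal in the two arms. Assume they show no FLI response and that the SD stays at 7.0. The difference becomes 8.96 × (1 − f). The required n per group becomes 9.57/(1 − f)², rounded up, then divided by 0.8 and rounded up again.

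| f | Difference | Power, 10 per group | Total N for 80% power with 20% loss |
|---|---|---|---|
| 0 | 8.96 | 82% | 26 |
| 10% | 8.06 | 73% | 30 |
| 20% | 7.17 | 63% | 38 |
| 30% | 6.27 | 52% | 50 |

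With the t distribution in place of the normal, the four powers are 77%, 68%, 58% and 47%. The pattern is the same.

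The documents give neither f nor the FLI response of patients without steatosis. The table is a sensitivity illustration, not an estimate.

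**The case against.** The strongest reply is that, read as a whole, the protocol does mean patients with fatty liver. Criterion 1 names steatohepatitis, two sections speak of an AFLD diagnosis, AFLD is defined by steatosis, and the FibroScan done at screening is described as detecting fat. An investigator may also exclude anyone on judgement. This stands as a statement of intent, and a reader who inferred that the protocol nowhere asks for fatty liver would go too far. It does not close the gap. Poster and social-media recruits are not required to bring a diagnosis, the evidence listed for criterion 1 contains no fat measure, and judgement is not a reproducible criterion.

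Further points limit the claim:

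- **Imaging wording.** The sentence that accepts "radiographic evidence of liver steatosis, fibrosis or cirrhosis, combined with abnormal biochemical results" concerns alcoholic liver disease in general. It cannot be used to say that AFLD may be diagnosed without steatosis.
- **Missing figures.** A figure in the algorithm and the study flow chart are not available. The statement about the algorithm covers the available text only.
- **The 90% figure.** One might infer from the Project Synopsis, which puts fat accumulation at 90% of heavy drinkers, that 10% of entrants will lack it. That figure covers all heavy drinkers, whereas entrants are selected for signs of steatohepatitis, so the complement does not transfer.
- **Zero FLI response.** The protocol describes FLI only as a 0–100 score on which higher means more steatosis. It does not say how FLI relates to CAP, so a response of exactly zero is an assumption.
- **Other outcomes.** Liver enzymes and liver stiffness are also primary outcomes, and patients can change on these whatever their CAP.

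**Conclusion.** The point holds as a gap between the stated disease and the written entry rules, and it should be fixed. The criteria and the available algorithm text allow a patient without steatosis, by the protocol's own threshold, to be randomised. The consequence is dilution of the FLI contrast and weaker conclusions about AFLD.

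The size is unknown. Under the assumptions of equal shares in the arms, no FLI response without steatosis, SD 7.0 and 10 evaluable per arm, power would move from about 82% to 73%, 63% or 52% for shares of 10%, 20% or 30%. The sample size arithmetic itself is correct.

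A reader might infer that the result would be biased or uninterpretable. The documents do not support that. Allocation is randomised 1:1 and double-blind, so such patients are not expected to favour either arm, and FLI, though used for sizing, is only one of several primary outcomes.

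**What to change.** Add an objective steatosis requirement at screening to inclusion criterion 1 and to the diagnostic algorithm, and apply it equally to clinic patients and general-public recruits. The CAP threshold above 263 in the Fibroscan section is the natural candidate, because the protocol already states it and the scan is already performed. The sponsor may justify another measure. At the same time, reconcile the inclusion and exclusion criteria and the algorithm with the AFLD definition in the Project Synopsis, the recruitment statements in the Methodology and background sections, and the Fibroscan section.

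The cost is one protocol amendment. If CAP is used, no new procedure is needed. The planned 26 can stay, because the assumed effect would then apply to patients with fatty liver. The downside is some screen failures and slower recruitment, in proportion to the share of candidates without steatosis. If that share is large, the burden on a single-site trial is real.
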